1. INTRODUCTION / SYNOPSIS

1.1 Phase

This is a Phase 2, single center study to treat low risk cutaneous squamous cell carcinomas (cSCC).

1.2 Indication

- Clinically consistent squamous cell carcinomas of the keratoacanthoma type and/or histologically confirmed other type of well-differentiated, low risk cSCC measuring > 0.5 cm to < 5 cm.
- Participants with cSCCs that are:

- Low risk, according to Brigham and Women Hospital's Tumor Staging(1) and the American Joint Committee on Cancer (Table 3),

- "Unresectable" based on a series of clinical scenarios that include:

1. Presence of co-morbidities that significantly influence the capacity of the patient to tolerate surgical procedures (e.g. significant stasis/edema in lower extremities lesions, patients predispose to wound dehiscence, etc.); and

2. Participant with multiple cSCCs that increase the surgical burden of complications or tolerance for these repeated procedures

3. Recurrent cSCC lesions after surgical intervention in areas where radiation treatment might be associated with increased complications

- 4. Participant declines surgery or other standard treatments for cSCC
- In the setting of study participants with tumor multiplicity, a maximum number of 3 cSCCs may be treated per anatomical site. In this clinical setting, the tumors will be required to be at least be 10 cm apart.

1.3 Endpoints

Primary Endpoint

The primary end point is to evaluate the overall response rate (ORR) defined as proportion of subjects who achieved complete response (CR) and partial response (PR) in the cSCC Target injected lesions (TILs).

Secondary Endpoints

- 1. Safety and adverse effect profile of talimogene laherparepvec in cSCC.
- 2. To measure time of response in cSCC TILs.
- 3. To measure the duration of overall response (DOR) of TILs.

- 4. Assess durable response rate (DRR) of TILs.
- 5. To measure the time to progression (TTP) of TILs.
- 6. Overall response rate (ORR) (CR+PR) assessed by imaging technique (high frequency ultrasound). This endpoint only applies to patients enrolled at the University of Arizona Cancer Center.
- 7. Overall clinical response rate (CR+PR) of individual TILs with talimogene laherparepvec (not as overall subject response).
- Overall clinical response rate (CR+PR) in cSCC Target non-injected lesion(s) (TNILs).

Exploratory Endpoint

The exploratory endpoint is to evaluate the abscopal effect of TVEC by determining the frequency of non-melanoma skin cancers 24 months prior to the TVEC injections (or Visit 1), 12 months prior to the TVEC injections (or Visit 1), as compared to the frequency of non-melanoma skin cancers 12 months after the TVEC injections (or Visit 4) and then 24 months after the last injection (or Visit 4) if available.

1.4 Patient Population

The patient population for this study will be non-immunocompromised patients presenting with at least one eligible cSCC. The TILs should be located in anatomical sites other than head and neck.

2. STUDY DESIGN

2.1 Phase

This is a Phase 2, single site, single arm study. All subjects enrolled in the study will be treated with talimogene laherparepvec.

2.2 Number of centers

There are two participating sites for this study: The University of Arizona Cancer Center and Honor Health Research Institute.

2.3 Number of subjects

There will be approximately 20 subjects participating in this protocol.

2.4 The subject participation time period

The subject participation period will be approximately 48 weeks. This will include a screening visit, 4 injection visits and 5 follow up visits. Total length of study/patient is 8.5 to 10.5 months.

Table 1. Visit Schedule

Screening Visit/V0

Selection of study TILs. Low-risk cSCC with at least 1 lesion > 0.5 cm to < 5 cm. TILs will have partial biopsies for confirmatory diagnosis. A total of up to 5 TILs per subject can be selected for treatment with no more than 3 lesions in one anatomical area. TILs in the same anatomical area will need to be 10 cm apart from the other injected lesions. A high frequency ultrasound of the TILs will be performed at baseline prior to starting first injection.

Selection of study TNILs. Lesions that are clinically suspicious of cSCC in the same anatomical location as TILs. Up to 10 TNILs can be followed with no more than 2 TNILs selected in the same anatomical area as a TIL. TNILs will have partial biopsies for confirmatory diagnosis. TNILs will be assessed by clinical measurement only without the use of ultrasound technique.

Visit 1: First Injection Visit: One to four (1-4) weeks after V0

- Target lesions (TILs and TNILs) are identified and documented with measurements and photographs. Photographs will be taken with regional and close up view of the anatomical area and lesion (Appendix A).
- Inject 0.1ml 4ml (based on TILs size section 7.1, Table 5) Talimogene laherparepvec at nominal concentration of 10⁶ plaque forming units (PFU)/mL with approximately 1.15 mL in a 2 mL vial for the initial dose. This will be administered intralesionally to 1-3 cSCC lesions per anatomical site with a maximum of 5 injectable lesions per patient.

Visit 2: Second injection visit: Three (3) Weeks after V1

- Target lesions are identified and documented with measurements and photographs. Photographs will be taken with global and close up view of the anatomical area and lesion (Appendix A).
- Inject 0.1ml 4ml (based on TILs size) and number of lesions selected.
 Talimogene laherparepvec at nominal concentration of 10⁸ PFU/mL with

approximately 1.15 mL in a 2 mL vial for the second and subsequent doses.

Visit 3: Third injection visit: Two (2) Weeks after V2

- Target lesions are identified and documented with measurements and photographs. Photographs will be taken with global and close up view of the anatomical area and lesion.
- Inject 0.1ml 4ml (based on TILs size) and number of lesions selected.
 Talimogene laherparepvec at nominal concentration of 10⁸ PFU/mL with approximately 1.15 mL in a 2 mL vial for the subsequent doses.

Visit 4: Fourth injection visit: Two (2) Weeks after V3

- Target lesions are identified and documented with measurements and photographs. Photographs will be taken with global and close up view of the anatomical area and lesion (Appendix A).
- Inject 0.1ml 4ml (based on TILs size) and number of lesions selected.
 Talimogene laherparepvec at nominal concentration of 10⁸ PFU/mL with approximately 1.15 mL in a 2 mL vial for the subsequent doses.

Visit 5: First Follow up visit: Four (4) weeks after V4

 Target lesions are identified and documented with measurements and photographs. Photographs will be taken with global and close up view of the anatomical area and lesion (Appendix A).

Visit 6: Second Follow up visit: Four (4) weeks after V5

 Target lesions are identified and documented with measurements and photographs. Photographs will be taken with global and close up view of the anatomical area and lesion (Appendix A). A repeat high-frequency ultrasound of target lesions will be completed to assess response from baseline.

Visit 7: Third Follow up visit: Six (6) weeks after V6

• Target lesions are identified and documented with measurements and photographs. Photographs will be taken with global and close up view of the

anatomical area and lesion (Appendix A).

Visit 8: Fourth Follow up visit: Fourteen (14) weeks after V7

• Target lesions are identified and documented with measurements and photographs. Photographs will be taken with global and close up view of the anatomical area and lesion (Appendix A).

Visit 9: Telephone Follow up: twelve (12) months after first injection (V1)

• Research coordinator will assess patient over the phone to determine if any changes have occurred to target lesions after V8.

3. OBJECTIVES

3.1 Primary Objective

1. To evaluate the ORR, defined as the proportion of subjects who achieved CR and PR in the cSCC TILs.

3.2 Secondary Objective

- To assess the safety and adverse effect profile of talimogene laherparepvec in low risk cSCC. This will be determined by incidence of all adverse events (AEs), grade ≥ 3 AEs, safety adverse events (SAEs), and events requiring the discontinuation of study drug, local effects on the tumor (ie, pain, inflammation and ulceration), and any clinically significant laboratory values.
- 2. To determine the time of response in cSCC TILs. This will be measured from the time from the first visit until objective tumor response (CR or PR) is identified.
- 3. To measure the duration of overall response (DOR) of TILs. This will be measured from the time measurement criteria are met for CR or PR (whichever status is recorded first) until the first date that recurrence or progressive disease (PD) is objectively documented, taking as reference for PD the smallest measurements recorded since the treatment started. If no recurrence or PD is documented after PR or CR is observed the time measurement will be performed at Visit 8.
- 4. To measure the durable response rate (DRR) of TILs. The duration of overall response is ORR lasting continuously for > than or equal to 6 months.

- To measure the time to progression (TTP) of TILs. This will be measured from the time treatment is initiated until the first date that recurrence or progressive disease (PD) is objectively documented, taking as reference for PD the smallest measurements recorded since the treatment started.
- 6. To measure the overall response rate (CR+PR) of TILs by high frequency ultrasound and correlate it with clinical overall response rate.
- 7. Overall clinical response rate (CR+PR) of individual TILs injected with talimogene laherparepvec (not as overall subject response).
- 8. To determine the overall clinical response rate (CR+PR) observed in TNILs that are present in the treated anatomical location (if applicable).

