9.4 Study Assessments

9.4.1 Tumor Measurements:

Tumor measurements will be done at each visit. Imaging assessment with high frequency ultrasound will be done at baseline and at the second follow-up visit (Visit 6). At baseline, up to 5 TILs that are at least 10cm apart will be selected to be followed over the course of the study. Up to 10 TNILs can be followed with no more than 2 TNILs selected in the same anatomical area as a TIL. Responses in TILs and TNILs will be measured serially. Clinical measurements will be performed with a millimeter measuring tape (Appendix A). All measurements will be selected that will be able to be followed clinically and for ultrasound evaluations. The RECIST 1.1 (Appendix B) response criteria will be used to evaluate tumor response. Individual tumor measurements will also be conducted to determine clinical management of TILs and TNILs. The timeframe for the clinical (primary endpoint) and evaluation will be at Visit 6 and for high-frequency ultrasound (secondary endpoints) at Visit 6 as well.

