9.4.1.1 Tumor Response

Complete Response (CR): Complete disappearance of all TILs (whether measurable or not, and no new lesions at the site of injection) confirmed by an assessment 8 weeks after the end of the injections (Visit 6).

Partial Response (PR): Decrease in tumor burden $\ge 30\%$ relative to baseline confirmed by an assessment 8 weeks after the end of the injections (Visit 6).

Duration of Overall Response (DOR): DOR is when the time measurement criteria are met for CR or PR (whichever status is recorded first) until the first date that recurrence or progressive disease (PD) is objectively documented, taking as reference for PD the smallest measurements recorded since the treatment started. If no recurrence or PD is documented after PR or CR is observed the time measurement will be performed at Visit 6 for PR and Visit 8 for CR.

Durable Response Rate (DRR): Measured from the time measurement criteria are met for CR or PR (whichever status is recorded first) with the response lasting continuously for > than or equal to 6 months. For PD, the reference will be the
smallest measurements recorded since the treatment started.

Time to progression (TTP): This will be measured from the time treatment is initiated until the first date that recurrence or progressive disease (PD) is objectively documented, taking as reference for PD the smallest measurements recorded since the treatment started.

Progressive Disease (PD): Progression is defined as >20% increase of at least 5 mm in the sum of the longest diameters of the target lesions or increase in tumor burden $\ge 20\%$ relative to nadir (minimum recorded tumor burden) or the appearance of one or more new lesions confirmed by an assessment 8 weeks after the end of the injections (Visit 6).

• **Rapid PD (RPD):** Is defined as an increase of >50% in tumor burden for lesions >2 cm in diameter or 100% tumor burden increase for lesion ≤2cm between visits.

Stable Disease (SD): Not meeting criteria for CR or PR, in absence of PD (Decrease of tumor size <30% to increase in size <20% of less than 5 mm in the sum of the longest diameters of the target lesions).

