9.4.1.2 Clinical Management of TILs and TNILs

Along with assessing the overall tumor response (see Section 9.4.1.1, Tumor Response), each individual lesion will be assessed to determine appropriate clinical management. The RECIST 1.1 (Appendix B) response criteria will also be used to evaluate each individual tumor response.

Individual Lesion Complete Response (IL-CR): Complete disappearance of target lesion (whether measurable or not, and no new lesion(s) at the site of the target lesion) confirmation by an assessment 8 weeks after the end of the injections (Visit 6).

Individual Lesion Partial Response (IL-PR): Decrease in tumor burden $\ge 30\%$ relative to baseline confirmed by an assessment 8 weeks after the end of the injections (Visit 6).

Individual Lesion Progressive Disease (IL-PD): Progression is defined as >20% increase of at least 5 mm in the sum of the longest diameters of the target lesions or increase in tumor burden $\ge 20\%$ relative to nadir (minimum recorded tumor burden) or the appearance of one or more new lesions confirmed by an assessment 8 weeks after the end of the injections (Visit 6).

 Individual Lesion Rapid PD (IL-RPD): Is defined as an increase of >50% in tumor burden for lesions >2 cm in diameter or 100% tumor burden increase for lesion ≤2cm between visits.

Individual Lesion Stable Disease (IL-SD): Not meeting criteria for CR or PR, in

absence of PD (Decrease of tumor size <30% to increase in size <20% of less than 5 mm in the sum of the longest diameters of the target lesions).

	Individual Lesion	Individual	Progressive Disease	Stable Disease
	Complete Response	Lesion Partial	(PD)	(SD)
	(IL-CR)	Response (IL-		
	IL-CR to be	PR)		
	determined at the latest by Visit 6 (8	 IL-PR will be followed and assessed at 	 If IL-PD confirmed in two consecutive visits OR at Visit 6 (8 week 	 IL-SD will be followed and assessed up to
	week follow up), and will be followed for 6	assessed at Visit 6 (8 week follow up)	OR at Visit 6 (8 week follow up), TIL will be withdrawn and	assessed up to Visit 6 (8 week follow up)
	months • No additional	 If IL-SD is documented at 	alternative therapeutic intervention given	 Alternative therapeutic

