9.5.1 Follow up

Visit 5- First follow up visit (28 +/- 7 days)

- Vital signs
- Review con meds
- Assess for any Adverse Events
- Skin exam limited to all target lesions
- Photograph and measure target lesions (Appendix A)
- Schedule the next follow up visit in 4 weeks.

Visit 6- Second follow up visit (28 +/- 7 days)

- Vital signs
- Review con meds
- Assess for any Adverse Events
- Skin exam limited to all target lesions
- Photograph and measure target lesions (Appendix A)
- Schedule second ultrasound to be completed on TILs before next follow up visit
- Schedule the next follow up visit in 6 weeks.

Visit 7- Third follow up visit (42 +/- 10 days)

- Vital signs
- Review concurrent meds

- Assess for any Adverse Events
- Skin exam limited to all target lesions
- Photograph and measure target lesions (Appendix A)
- Schedule the next follow up visit in 14 weeks.

Visit 8 - Fourth follow up visit (98 +/- 21 days)

- Vital signs
- Review con meds
- Assess for any adverse events
- Skin exam limited to all target lesions
- If sites are free of disease, participant participation will be complete
- Photograph and measure target lesions (Appendix A)
- Complete subject payment form

Visit 9 – Telephone Follow up (356 +/- 31 days) after Visit 1

• Assess for changes of target lesions

• If active lesion(s) are noted by the participant, they will follow up with a dermatologist and their records will be requested

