16.2.2 Safety and Adverse effects of talimogene laherparepvec in cSCC

Summary statistics (counts, percentage, mean, standard deviation, etc.) will be presented for the safety and adverse endpoint as appropriate. Grading of adverse effects will be done as per CTCAE 4.03 grading of the National Cancer Institute.

16.2.3 Duration of overall response (DOR) of TILs.

Once a PR or CR has been established, the analysis will consist of Kaplan-Meier estimates. The analysis will also include a median and a 95% 1-sided exact confidence interval.

16.2.4 Durable Response Rate of TILs.

Once a PR or CR has been established, the analysis will consist of Kaplan-Meier estimates. We will consider durable response when continuously PR or CR is sustained for at least 6 months. The analysis will also include a median and a 95% 1-sided exact confidence interval.

16.2.5 Time to progression (TTP) of TILs.

The analysis of time to response will consist of Kaplan-Meier estimates. The median time and 95% confidence interval will be presented.

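### A response first recorded at Visit 6 cannot be shown by examination to last the 6 months that durable response requires, because Visit 8, the last measured visit, comes only 20 weeks later

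*Combined protocol and SAP*

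**What the plan says.** **Definition.** Section 3.2, item 4, repeated in 16.1.2, reads "The duration of overall response is ORR lasting continuously for > than or equal to 6 months". Section 9.4.1.1 counts from the first recorded CR or PR, "with the response lasting continuously for > than or equal to 6 months". Section 16.2.4 adds "We will consider durable response when continuously PR or CR is sustained for at least 6 months" and plans Kaplan-Meier estimates with a median and a one-sided 95% exact interval.

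**Start of the clock.** Section 9.4.1 says "Tumor measurements will be done at each visit", so a response can be recorded before Visit 6, the visit used for the primary endpoint.

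**Schedule.** Visit 7 follows Visit 6 by six weeks. The next entry in Table 1 (section 2.4) is "Visit 8: Fourth Follow up visit: Fourteen (14) weeks after V7". Visit 8 is the last visit with a skin examination and measurements (9.3, 9.5.1 and the schedule in section 26). Visit 9 is a telephone call about twelve months after Visit 1.

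**End of the clock.** With no recurrence or progression, item 3 of sections 3.2 and 16.1.2 takes duration to Visit 8. Section 9.4.1.1 takes it to Visit 6 for PR and to Visit 8 for CR.

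**Related text.** Table 7 (9.4.1.2) has an individual complete response settled by Visit 6 at the latest and then followed for 6 months. Section 9.5.1 says of Visit 8: "If sites are free of disease, participant participation will be complete".

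**The concern.** Definition and schedule do not fit each other. A subject whose response is first seen at Visit 6 runs out of examinations before 6 months have passed, however well the response holds. Whether a subject can be observed as durable then depends partly on how early the response was noted and on where visits fall in their windows, as well as on how long the response lasts. Durable response rate is a named secondary endpoint, so a reader of the results would take it as a statement about durability alone. Table 7 shows that 6 months of follow-up after a Visit 6 complete response was intended, yet no examination falls late enough to supply it.

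**Working it through.** **Inputs.** Intervals after the previous visit, with windows (sections 2.4, 9.3, 9.5.1, 9.7): V2 21 ± 3 days, V3 14 ± 3, V4 14 ± 3, V5 28 ± 7, V6 28 ± 7, V7 42 ± 10, V8 98 ± 21. Visit 9: 356 ± 31 days after Visit 1.

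**Check against the plan's own figure.** V4 to V6 = 28 + 28 = 56 days = 8 weeks, which matches section 9.4.1.1.

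**Nominal days from Visit 1.** V2 21, V3 35, V4 49, V5 77, V6 105, V7 147, V8 245.

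**Threshold.** The documents do not convert 6 months to days. Calendar months give 181 to 184 days, and 26 weeks gives 182. Half of the plan's own 356-day year is 178.

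**Longest response that can be observed by examination.** Nominal = 245 minus the day of first recording. Range = nominal ± the sum of the later windows.

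| First recorded at | Nominal days to V8 | Sum of windows | Range | 6 months reachable? |
|---|---|---|---|---|
| V2 | 245 − 21 = 224 | 51 | 173–275 | Yes, nominally |
| V3 | 245 − 35 = 210 | 48 | 162–258 | Yes, nominally |
| V4 | 245 − 49 = 196 | 45 | 151–241 | Yes, nominally |
| V5 | 245 − 77 = 168 | 38 | 130–206 | Only if visits run late |
| V6 | 245 − 105 = 140 | 31 | 109–171 | No |

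For V6 the nominal shortfall is 182 − 140 = 42 days. With both later windows fully extended it is still 181 − 171 = 10 days, and 171 is also below 178. For V5, visits would have to run 182 − 168 = 14 days late in total, out of 38 available.

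**PR under section 9.4.1.1.** If the PR clock stops at Visit 6, a PR recorded as early as Visit 2 has 105 − 21 = 84 nominal days. Adding all later windows (3 + 3 + 7 + 7 = 20) gives 104. No PR could be durable under that sentence.

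**Effect on the planned analysis.** Under Kaplan-Meier, an unrelapsed V6 responder is censored at about day 140 and a V5 responder at about day 168. Beyond day 168 on the nominal schedule the curve rests only on subjects whose response was recorded by Visit 4. Reading it as the 6-month durability of all responders assumes that late responders relapse at the same rate as early ones, and these data cannot test that between days 140 and 182. If DRR is instead reported as a crude proportion, as its name suggests, the same late responders count as non-durable. The documents do not say whether a proportion will also be given.

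**Visit 9.** V6 to V9 is 356 − 105 = 251 days nominally. The shortest gap is (356 − 31) − (105 + 3 + 3 + 3 + 7 + 7) = 325 − 128 = 197 days. The call is beyond 6 months but takes no measurement.

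**The case against.** **The endpoint still works for many responders.** The clock starts at first recording and lesions are measured at every visit, so responses noted by Visit 4 can reach 6 months. This stands. A reader might infer that secondary objective 4 cannot be answered; the documents do not support that.

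**Late responders are not failures under the plan.** A reader might compute how far DRR would fall if every late responder counted as non-durable. Section 16.2.4 plans Kaplan-Meier, which censors them. If no one relapses, the 6-month estimate stays at 100% of responders as long as some early responder is still at risk. The documents also give no share of late responses, so no size of fall follows from them. What remains is lost precision and dependence on early responders.

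**Visit 9 looks past 6 months.** It asks about changes in target lesions after Visit 8, and if the participant reports an active lesion, dermatology follow-up is arranged and records are requested. This has some weight for CR. But no section assigns the call to durable response, and 3.2 and 16.1.2 end the duration clock at Visit 8. It cannot support a continuing PR either, because Table 7 provides for other treatment to be offered at Visit 8.

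**Complete responders may still be called.** A reader might infer from the Visit 8 sentence in 9.5.1 that disease-free participants lose the call. Against that, section 2.4 counts five follow-up visits, section 26 lists the call without any condition on disease status, and 9.8 keeps subjects on study until follow-up visits are done. This is a conflict of wording, not shown loss of data.

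**Conclusion.** The mismatch is real but limited. A response first recorded at Visit 6 has at most 171 days of examined follow-up and cannot be shown to last 6 months. One first recorded at Visit 5 can be only when visits run late. Earlier responses qualify on the nominal schedule. Durable response as written therefore depends partly on when response was first recorded. Separately, section 9.4.1.1 contradicts 3.2 and 16.1.2 on when PR duration ends, and on its wording no PR could be durable.

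The primary ORR, assessed at Visit 6, and the two-stage decision are unaffected, and no hypothesis test is planned for durable response.

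The conclusion assumes that 6 months means about 178 days or more, that windows run from the previous visit, and that a telephone report does not establish continued response. If 6 months were read as 24 weeks (168 days), which the documents do not say, Visit 5 responses would just qualify nominally and Visit 6 responses only at the extreme of the windows.

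**What to change.** 1. In 3.2, 9.4.1.1, 16.1.2 and 16.2.4, define durable response as CR or PR present at Visit 6 and still present at Visits 7 and 8. Label it about 20 weeks (109 to 171 days within windows) instead of 6 months. All responders are then judged over the same visits.
2. In 9.4.1.1, use Visit 8 as the end of the duration clock for both CR and PR, in line with 3.2 and 16.1.2.
3. In 16.2.4, say whether durable response is reported as a proportion or from Kaplan-Meier, since the two treat late responders differently.
4. Reconcile Table 7's 6-month follow-up with the visit schedule, and the 9.5.1 sentence on completing participation at Visit 8 with the Visit 9 call in 2.4, 9.5.1 and section 26.

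These are wording changes with no added visits. The cost is a shorter durability claim.

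If the sponsor prefers to keep 6 months for responses first recorded at Visit 6, an examination would be needed at least 26 weeks after that visit, about 6 weeks later than the nominal Visit 8. Visit 8 also triggers steps in Table 7 and section 7.4, so the schedule and those sections would have to be reconciled with the definition. That would be a larger amendment with longer follow-up per subject.
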